7.2. Study Population and Setting

Information on the 5 participating RPs is described below in Section 7.4.

Members of participating US-based health plans \geq 50 years of age will be eligible for inclusion in the evaluation of each outcome if all of the following criteria are met:

- 1. Evidence of receipt of a single dose *Arexvy*.
- 2. 365 days of continuous medical and pharmacy enrolment, allowing up to 45-days' gap, prior to *Arexvy* receipt.
- 3. For evaluation of GBS and ADEM cases: Continuous enrollment through the end of the respective control interval and extra days except in case of death after *Arexvy* vaccination.
- 4. For evaluation of AF cases: Continuous enrolment through the Day 106 postvaccination, except in case of death after *Arexvy* vaccination.
- 5. For each outcome: First-in-365-days case of the outcome in the risk or control interval (i.e., definition of an incident case).
- 6. No evidence of a second dose of *Arexvy* during the follow-up period.
- 7. No evidence of administration of another medical product indicated for RSV disease prevention (i.e., vaccine from different manufacturer or a monoclonal antibody to prevent RSV lower respiratory tract disease) prior to the index *Arexvy* vaccination or during the follow-up period.

Patients will be required to be enrolled throughout the risk and control windows combined, plus an extra 7 days for GBS and ADEM analyses, and an extra 90 days for AF analysis. This study will include outcomes of interest among people who die during the full window. The number of events, if any, that were among people who died during follow-up will be quantified. See Section 7.7.2.1 for additional details regarding inclusion of those who died in the inferential analyses.

Health plan members eligible for inclusion in research activities, including chart review, will be included.

Illustrations of temporal inclusion criteria for SCRI analyses are shown Figure 1, Figure 2, and Figure 3 below. The red star in each figure indicates occurrence of an outcome of interest.

Figure 1 Illustration of SCRI study design for new-onset GBS and ADEM outcomes

*In the primary analyses, cases with symptom onset (established from chart review) in the control window may present with coded diagnoses (identified in claims data) up to 7 days after the end of the control window ('extra days'). Date of symptom onset is deemed as the date of chart confirmed events. Only events with dates of symptom onset in risk and control windows contribute to the primary analyses.

**Post-index enrolment requirement does not enforce survival through the end of all evaluation windows postvaccination. Vaccinated cases with evidence of death in the post-index window will contribute to the analyses.

Figure 2 Illustration of SCRI design for new-onset AF¹ (example with 1 inpatient diagnosis code)

Vaccine (day 0)		
Baseline (day –365, -1)			
Study selection criteria; participant characterization		*	
	Risk window (day 1,8)	Control window (day 9,16)	
Pre-index enrollment (gaps up to 45 days allowed)	Post-index e (no gaps all	enrollment* owed)	
· · · · · · · · · · · · · · · · · · ·		r N	

†Analyses will be claims-based if estimated PPV from descriptive monitoring queries is ≥80% and chart- confirmed if PPV <80%.

*Post-index enrolment requirement does not enforce survival through the end of all evaluation windows postvaccination. Vaccinated cases with evidence of death in the post-index window will contribute to the analyses.

Figure 3 Illustration of SCRI design for new-onset AF^I (example with 2 outpatient or ED diagnosis codes) ^{II}

†Analyses will be claims-based if estimated PPV from descriptive monitoring queries is ≥80% and chart- confirmed if PPV <80%.

* Post-index enrolment requirement does not enforce survival through the end of all evaluation windows postvaccination. Vaccinated cases with evidence of death in the post-index window will contribute to the analyses. Abbreviations: AF: atrial fibrillation; ED: emergency department; PPV: positive predictive value.

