However, such an approach introduces a potential bias toward identifying an increased risk, or a bias toward finding more cases earlier rather than later in the follow-up, as the incidence criterion becomes more stringent later in the evaluation window than it is in the earlier period of follow-up closer to the date of vaccination. The lengths of risk and control windows are defined below (Table 4) for each outcome and are based on biologic plausibility, published results, and prior vaccine safety studies [Arya, 2019; Goud, 2021; [Britton, 2024; Lloyd, 2024]. For all outcomes studied, control windows will be after risk windows rather than before the index vaccination as some individuals may delay or not get vaccinated following certain illnesses [Jackson, 2006], which would produce a bias toward identifying an increased risk if the control window were before vaccination.

The overall study will include annual, cumulative monitoring queries, a final inferential analysis evaluating new-onset AF, and a final inferential analysis evaluating GBS and ADEM. The timing of monitoring queries will depend on data availability and other factors and are expected to be annual. The data sources are described in Section 7.4 below.

During the course of the study, there will be descriptive annual monitoring queries conducted to track uptake of *Arexvy*, describe vaccinees, and assess numbers of outcomes of interest. Operationally, for the first monitoring query, *Arexvy* vaccine uptake will be assessed from **CO** (the month when vaccinations began) through February 2024; subsequent queries will be cumulative from **CO**. The maximum amount of time from vaccination to outcome identification is 91 days for GBS and ADEM (events will be identified through the risk window, control window, and extra days; extra days will be used to ensure that we capture potential events that had a symptom onset during the control window but a diagnosis code recorded later), and 106 days for new-onset AF definition (for new-onset AF, if the first qualifying diagnosis code occurs on Day 16, then the last possible second code would be on Day 106). See Table 4 for details of the algorithms.

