Medical records will be obtained from participating RPs in a manner compliant with the Health Insurance Portability and Accountability Act (HIPAA) and local privacy regulations. Hospital and outpatient charts will be obtained directly through requests from RPs using identifiers obtained from administrative claims data. Designated protected health information users at each RP will link the protected health information with masked patient identification numbers, dates of birth, and provider information for the patients identified for medical record abstraction. As noted above, charts are not expected to be 100% obtainable from participating RPs and that ~30% of charts sought can be unobtainable based on prior experience. Section 7.7.2 includes description of how potential events with unobtainable charts will be handled in the analyses. Bias will not be expected based on whether charts were obtainable or unobtainable (reasons for charts being unobtainable include providers being non-responsive or providers incorrectly assuming patient authorization is required). Table 4 below summarizes the proposed diagnosis code-based case-finding algorithms and key elements of the validation of each outcome.

Table 4 Case-finding algorithms and risk and control windows for outcomes of interest

Outcome	Diagnosis code(s) to identify event	Event identification care setting and details	Risk window	Control window, Extra days	Look-back period for outcome-free window	Diagnosis code(s), care setting for outcome-free period	Published algorithm data	Chart review considerations
New- onset GBS	G61.0 ^a	CC1	Primary: 1-42 days [Sejvar, 2011; Goud, 2021; Britton, 2024 Lloyd 2024]	Control window: 43-84 days, Extra days: 7	-365 through - 1 (day 0 is day of event), as previously conducted [Polakowski, 2013]	G61.0 or G65.0, inpatient setting (any position)	 PPV from studies using Medicare data: (1) 78.57% (95% CI, 63.37%- 93.77%) [Goud, 2021] (2) 71.21% (95% CI: 63.49%-78.94%) 	Will seek charts on all events. Final analysis will include chart- confirmed events only.
			Sensitivity: (a) 1-21 days and (b) 8-28 days				[Arya, 2019]; (3) 68.0% (95% CI: 56.8%- 77.5%) [Lloyd, 2024]	

220149 (EPI-RSV-041 OA VS US DB) Protocol Amendment 2 Final

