7.3.2.2. Ascertainment and confirmation of GBS events

Screening for GBS:

Within each RP's database, patients will be identified as having possible GBS within 91 days after *Arexvy* vaccination (primary analysis risk window days 1-42, control window days 43-84, and 7 extra days) if they had either:

. The claims-based

case date for cases will be based on the earliest diagnosis of interest. New-onset GBS will be identified by requiring that there is no evidence of GBS in the 365 days prior to the first diagnosis code of interest: no occurrence of G61.0 (GBS) or G65.0 (Sequelae of GBS) hospital discharge diagnosis (any position) in days -365 through day -1 (day 0 is the day of the event).

The primary risk window will be 42 days as several prior vaccine safety studies of postvaccination GBS have used a 42-days window [Arya, 2019; Goud, 2021; Britton, 2024; Lloyd, 2024], and that precedent will be followed. Sensitivity analyses using risk windows of (a) days 1-21 and (b) days 8-28 will be included based on the timing of postmarketing reports of GBS, other studies of post-vaccination GBS [Klein, 2021], and the timing of the 1 reported GBS case in the *Arexvy* clinical trials [Melgar, 2023].

The control window will be days 43-84 following vaccination for both primary and sensitivity analyses' risk windows. Continuous enrolment will be required through the end of the respective control interval plus 7 extra days to ensure that diagnosis codes that are recorded after symptom onset (and potentially after the risk and comparison windows) are captured. The final analyses will include individuals with an event of interest and who die during the 91-days follow-up period.

Validation of GBS events:

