certainty	
Level 1 (Highest Level of Certainty)	Bilateral AND flaccid weakness of the limbs. Decreased or absent deep tendon reflexes in weak limbs. Monophasic illness pattern AND interval between onset and nadir of weakness between 12h and 28 days AND subsequent clinical plateau. The eventual outcome is either stabilization at nadir OR subsequent improvement OR death. Electrophysiologic findings consistent with GBS. Cytoalbuminologic dissociation (i.e., elevation of CSF protein level above laboratory normal value AND CSF total white cell count <50 cells/µL). Absence of identified alternative diagnosis for weakness.
Level 2	Bilateral AND flaccid weakness of the limbs. Decreased or absent deep tendon reflexes in weak limbs. Monophasic illness pattern AND interval between onset and nadir of weakness between 12h and 28 days AND subsequent clinical plateau. CSF total white cell count <50 cells/µL (with or without CSF protein elevation above laboratory normal value) OR If CSF not collected or results not available, electrophysiologic studies consistent with GBS. Absence of identified alternative diagnosis for weakness.
Level 3	Bilateral AND flaccid weakness of the limbs. Decreased or absent deep tendon reflexes in weak limbs. Monophasic illness pattern AND interval between onset and nadir of weakness between 12h and 28 days AND subsequent clinical plateau. Absence of identified alternative diagnosis for weakness.
Level 4 (Lowest Level of Certainty)	A case will be classified as having "insufficient evidence" if a physician's diagnosis of GBS is made, but evidence is insufficient to classify the patient at any higher level of diagnostic certainty (i.e., the abstraction data for that case does not contradict any of the Level 3 criteria but is missing information for at least one of the Level 3 criteria). Absence of identified alternative diagnosis for weakness.
220149 (EPI-RSV-041 OA VS US DB) Protocol Amendment 2 Final

Brighton level of diagnostic	Criteria
certainty	
Level 5 (Not a case)	If a case does not meet the criteria necessary for classification as Brighton Level 1, 2, or 3, is not diagnosed as GBS by a physician, or has a definitive alternate diagnosis documented in the chart, the patient will be classified as "not GBS."

Abbreviations: CSF: cerebrospinal fluid; GBS: Guillain-Barré syndrome; h: hours.

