7.7.2. Primary analysis

7.7.2.1. Main analytical approach

SCRI-based analyses of primary and secondary objectives will include the *Arexvy* vaccinees with an event of interest in the risk window, control window, or the extra days after the control. In these analyses, each individual serves as their own control. IRRs of the outcomes will be estimated with 95% CIs using conditional Poisson regression models. All SCRI-based analyses will use conditional Poisson regression. A forthcoming SAP will be finalized prior to conducting the inferential analyses.

Analysis of the primary GBS and ADEM outcomes will be based on chart-confirmed cases as has been previously done [Arya, 2019]. For those outcomes, onset of symptoms will be discerned from medical record review and date of the event will be classified based on expert clinician adjudication. Identification of all events in days 1 through 91 after vaccination will be included in the medical record review but which window (risk, control, extra days) the events are counted in for the analysis will be determined based on the symptom onset date from the medical record. Events identified in the claims data with unobtainable charts will be excluded from the primary analyses due to concerns about misclassification of the outcome and timing of onset of symptoms.

As previously noted, events among people who die during the follow-up window (risk window, control window, or during the extra days) will be included. The number of events will be quantified, if any, that were among people who died during follow-up. The final analyses will include individuals who die during the risk or control intervals.

Follow-up time will be artificially continued until the last day of the control interval, which will avoid including fatal cases that occurred in the control interval over fatal cases that occurred in the risk interval. If a fatal event occurs during the risk window, all the remaining days in the risk window and all the days that would have occurred in the control window will be included in the analyses.

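### The Day 91 search limit gives control-window GBS and ADEM onsets less time to be coded than risk-window onsets, so any case lost to late coding pushes the primary IRR upward by an amount the protocol does not allow one to estimate.

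*Protocol*

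**What the plan says.** Protocol 7.1 sets the limit of the search: "The maximum amount of time from vaccination to outcome identification is 91 days for GBS and ADEM". Table 4 gives the GBS and ADEM windows as "Control window: 43-84 days, Extra days: 7", after a risk window of days 1-42. Section 7.3.2.2 repeats "primary analysis risk window days 1-42, control window days 43-84, and 7 extra days", and 7.3.2.3 follows it for ADEM. Section 7.2 requires enrolment through both windows "plus an extra 7 days for GBS and ADEM analyses".

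Finding a case and placing it use different dates. Claims find it: "Identification of all events in days 1 through 91 after vaccination will be included in the medical record review" (7.7.2.1). The adjudicated onset date places it: "Only events with dates of symptom onset in risk and control windows contribute to the primary analyses" (footnote to Figure 1).

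The sensitivity analyses leave the control period and the extra days alone. For GBS, "The control window will be days 43-84 following vaccination for both primary and sensitivity analyses' risk windows"; 7.3.2.3 keeps the same control window for ADEM. The other GBS and ADEM analyses in 7.7.2.3 change the case set, exclude immunocompromised patients or, for GBS, adjust for season.

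Section 7.1 explains the extra days as a way to capture control-window onsets that are coded later. No reason for choosing 7 days and no lag data are given.

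**The concern.** The time available for a case to be found depends on where its onset falls, and it is shorter throughout the control window than anywhere in the risk window. This is unequal ascertainment between the two periods being compared. Chart review cannot repair it, because the chart of a case coded after Day 91 is never requested.

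The protocol accepts the opposite principle elsewhere. Section 7.1 defends its first-in-X-days rule on the ground that a case should have the same chance of being found wherever it falls in follow-up, and warns against rules that favour early cases. For atrial fibrillation (AF), 7.3.2.4 requires enrolment through Day 106, 90 days past the control window, so that vaccinees have equal time for a second code.

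At stake is an upward shift in the primary safety estimate, possible with no vaccine effect at all, that no planned analysis would reveal.

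**Working it through.** **1. The plan's own figure.** Protocol 7.5 and Table 8 state 69 GBS cases for RR 2, 80% power, two-sided alpha 0.05 and equal windows. With the signed-root likelihood-ratio formula for self-controlled case series, p = 2/3:

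- A = 2[p ln 2 - ln 1.5] = 0.113
- B = (ln 2)^2 p(1-p)/A = 0.943
- n = (1.960 + 0.842 x sqrt(B))^2 / A = 68.09, rounded up to 69.

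The 23 control cases at 4.5 per 100 000 person-years need 23 / (0.000045 x 42/365.25) = 4 444 841 vaccinees; Table 8 gives 4 444 842. The figure reproduces. It assumes equal ascertainment in the two windows.

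**2. Time to be coded = 91 - onset day.**

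| Onset day | Window | Days left |
|---|---|---|
| 1 | risk | 90 |
| 42 | risk | 49 |
| 43 | control | 48 |
| 84 | control | 7 |

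**3. Loss at a fixed lag, with no distribution assumed.** If every case had lag k, onsets after day 91 - k would be missed: none at 7 days, 3 of 42 control onset days at 10 days (7%), 7 of 42 at 14 (17%), 14 of 42 at 21 (33%) and 21 of 42 at 28 (50%). The risk window loses none of these.

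**4. Loss over assumed lag distributions.** The document gives none, so these are assumptions. With onset uniform within each window:

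- Loss in control, L_C = mean over d = 43..84 of P(lag > 91 - d)
- Loss in risk, L_R = the same mean over d = 1..42
- IRR factor = (1 - L_R) / (1 - L_C)

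The lower value in each range counts Day 91 in full (92 - d in place of 91 - d).

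| Assumed lag | L_C, 7 extra days | IRR factor, 7 extra days | IRR factor, 28 extra days |
|---|---|---|---|
| none above 7 days | 0 | 1.00 | 1.00 |
| exponential, mean 3 | 0.6-0.8% | 1.01 | 1.00 |
| exponential, mean 5 | 2.7-3.2% | 1.03 | 1.00 |
| exponential, mean 7 | 5.7-6.6% | 1.06-1.07 | 1.00 |
| exponential, mean 10 | 11.1-12.2% | 1.12-1.14 | 1.01-1.02 |
| lognormal, median 5, sigma 0.8 | 4.5-5.3% | 1.05-1.06 | 1.00 |
| lognormal, median 7, sigma 0.8 | 8.9-10.1% | 1.09-1.11 | 1.01 |
| lognormal, median 10, sigma 0.8 | 16.2-17.8% | 1.18-1.20 | 1.03 |

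L_R is below 1% in every row.

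**5. False-signal rate for GBS, 69 cases, no true effect.** With inflation f, the risk-window count is Binomial(69, f/(1+f)). The protocol does not fix the test, so two cut-offs are shown: 43 (43 against 26 gives Wald z = 2.03) and 44 (the exact two-sided p is 0.053 at 43 and 0.029 at 44).

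| f | P(43 or more) | P(44 or more) |
|---|---|---|
| 1.00 | 2.7% | 1.5% |
| 1.06-1.07 | 4.5-4.9% | 2.7-2.9% |
| 1.12-1.14 | 7-8% | 4.4-5.1% |

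**The case against.** The strongest reply concerns size. No onset-to-admission lag is in the protocol, and 7.3.2.1 dates inpatient claims by admission, which shortens the lag that matters. With short lags the bias is under 1% or nil. With 69 cases the standard error of the log IRR near the null is about sqrt(2/34.5) = 0.24, so a 7% inflation (ln 1.07 = 0.068) is about 0.28 of a standard error. The extra days show that delayed coding was considered, and 7.9 allows for possible quantitative bias analysis of imperfect sensitivity. All of this stands, and it keeps the point modest. It does not remove it: the direction is fixed by the windows, and neither 7.7.2.3 nor 7.9 names the unequal search time.

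Three stronger readings are tempting and not supported.

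- A reader might take the criterion in Table 5, "interval between onset and nadir of weakness between 12h and 28 days", as evidence of late admission. It shows only that slowly progressing GBS can be confirmed. Patients may be admitted before nadir, and the ADEM criteria in Table 6 contain no such limit.
- A reader might infer that all late-diagnosed control-window cases are lost. Only those whose lag exceeds 91 minus the onset day are; onsets on days 43-63, half the window, still have 28 to 48 days.
- A reader might infer a known bias in both primary outcomes. The mechanism applies to both, but the size is unknown for both. For ADEM, Table 8 plans 2 control cases of 12, so even an 11% loss is an expected 0.2 of a case, against a target RR of 7.

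It can also be said that 28 days does not equalise the search: risk onsets would have at least 70 days and control onsets 28 to 69. That is true, and it is why the common-lag analysis belongs beside it.

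**Conclusion.** The asymmetry holds on the protocol's own windows, and its direction is upward whenever control-window cases are lost. Its size is an assumption: nil if no lag exceeds 7 days, about 1-14% for exponential mean lags of 3 to 10 days, and up to about 20% for the longest lognormal lag examined. These figures rest on onset being uniform within windows and on the lag being the same in both. The documents do not show that the primary IRR will be materially biased. They do show an avoidable bias in one direction, in both primary safety outcomes, with nothing planned that would detect it. Because the remedy is cheap, it should be made.

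**What to change.** 1. Change the GBS and ADEM extra days from 7 to 28, so that the claims search and required enrolment run through Day 112. Amend Table 4, Sections 7.1, 7.2, 7.3.2.2, 7.3.2.3 and 7.7.2.1, and Figure 1. Keep the rule that only onsets on days 1-84 count.
2. Report the observed onset-to-code lag from the charts, by window.
3. Add a sensitivity analysis that counts only cases coded within one common maximum lag of onset in both windows. Under the current search that maximum is 7 days (84 + 7 = 91). It removes the asymmetry exactly, at the price of fewer cases.

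The cost is 21 more days of required enrolment and of the exclusion period for a second dose or another RSV product, which loses a few members. Data cuts move slightly later, and a few more charts are requested, most with onset after Day 84. Day 112 is six days past the AF requirement of Day 106, and inpatient claims already need about 6 months to mature.

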7.3. Variables

7.3.1. Exposure definitions

Exposure will be identified by evidence of receipt of one dose of *Arexvy* via procedure or pharmacy dispensing codes (e.g., CPT, NDC, Healthcare Common Procedure Coding System [HCPCS] codes) or if state immunization system data are available at any RP, CVX codes will be included. Duplicate codes that are expected to be erroneous (i.e., a second code for *Arexvy* within Days 0-7) will be ignored. Only a patient's first recorded dose will be included. Since the current recommendation for *Arexvy* administration is as a one-time dose, we do not anticipate many second doses, though people with evidence of a second dose during the follow-up period will be excluded (i.e., Day 8 through follow-up). If codes for both *Arexvy* and another medical product indicated for RSV disease prevention (i.e., a code for a different manufacturer's RSV vaccine or monoclonal antibody to prevent RSV lower respiratory tract disease) are identified prior to the index *Arexvy* or through follow-up, such individuals will be excluded from the study.

Code Type	Code	Description
CVX	303	Respiratory syncytial virus (RSV), vaccine, recombinant, protein subunit RSV prefusion F, adjuvant reconstituted, 0.5 mL, preservative free
СРТ	90679	Respiratory syncytial virus vaccine, preF, recombinant, subunit adjuvanted, for intramuscular use
NDC	58160-848-11	Respiratory syncytial virus vaccine antigen/AS01E adjuvant/PF (Arexvy [Pre- fusion F protein])
NDC	58160-723-03	Respiratory syncytial virus vaccine, antigen 2 of 2 (Arexvy Antigen Component)
NDC	58160-744-03	Vaccine adjuvant system, AS01E/PF, component vial 1 of 2 (Arexvy Adjuvant Component [Pre-fusion F protein])

Table 2Codes for Arexvy

Abbreviations: CPT: Current Procedural Terminology; CVX: Vaccine administered code; NDC; National Drug Code.

